2.4. Definition of Subgroups

[Table 8](#) defines subgroups of interest for investigation across several efficacy, safety, virology and other analysis endpoints (type of analysis = data domains). Refer to [Section 5](#) for a detailed overview of efficacy endpoints (primary, secondary and exploratory).

The following data handling applies to subgroup presentation:

- With the exception of Region [Class 1], subgroups will only be presented if, based on total number of subjects across treatment groups:
 - Subgroups with two strata: N = 36 in both strata
 - Subgroups with more than two strata: N = 36 in at least one stratum
 Aforementioned data handling results in approximately 12 subjects minimum per treatment group with data in a stratum. This minimum number of subjects ensures sufficient data for meaningful subgroup analysis.
- Symptom onset:
 - Cohort 1: unless otherwise specified for a given endpoint, exploratory endpoints, as detailed in [Section 5.4](#), will only be analyzed in the stratum: subjects with symptom onset ≤ 3 days before randomization. Subsequent subgroup analyses will be performed within this stratum only and also considering meaningful number of subjects as previously described.
 - In case of population enrichment decision (subjects with symptom onset ≤ 3 days before randomization), efficacy analyses will focus on those subjects with symptom onset ≤ 3 days before randomization stratum only. Subsequent subgroup analyses will be performed within this stratum only and also considering meaningful number of subjects as previously described.

- **Table 8** provides a general overview of the subgroups to be investigated per type of analysis (data domain). For any given type of analysis, subgroup presentation will not be performed for all endpoints within the given domain but will be focused on the key outputs only. For example, 2 = viral load and 3 = clinical course endpoints below, all subgroups indicated in **Table 8** will only be analyzed and presented for the primary endpoint and key clinical course endpoints (i.e. endpoints included in previous decision-making).
- Subgroup analysis and presentation may comprise tabulation of results and/or graphical presentation as best suits the purpose of the subgroup investigation. Specific details of- and format of subgroup analyses will be detailed in a separate document (data presentation specifications [DPS]) and is not included within the scope of this SAP.

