5.1.1. Level of Significance

The primary objective is to establish antiviral activity of JNJ-53718678. The primary efficacy endpoint is the RSV RNA viral load AUC from immediately prior to first dose of study drug through Day 5 ($AUC_{Day\ 5}$) derived from the RSV RNA viral load as measured by a qRT-PCR assay in nasal swabs. A hybrid methodology that combines aspects of multiple testing with modeling techniques (MCP-Mod) will be used for evaluating dose-

response trends and estimating the dose-response relationships. The dose-response will be tested at each (interim) analysis at alpha=2.5% (1-sided).

The primary analysis will only adjust for multiplicity with respect to the candidate models included into the MCP-Mod test. Due to the exploratory nature of the study, no adjustment for multiplicity due to sub-populations and adaptations will be considered in the primary analysis. A secondary analysis approach will be performed to control for multiplicity in the clinical course endpoints and for adaptations (see Section [5.2.3.2](#)).

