5.2.3. Analysis Method

Mean \log_{10} RSV RNA viral load values over time will be analyzed using a restricted maximum likelihood based repeated measures approach (MMRM). The analysis model includes fixed (discrete) effect parameters for treatment, randomization stratification factors (derived), analysis visit and treatment-by-analysis visit interaction, as well as continuous covariates for baseline \log_{10} viral load and baseline \log_{10} viral load-by-analysis visit interaction. An unstructured (co)variance structure will be used to model the within-subject errors. In case this model will not converge, the Toeplitz covariance structure will be applied. The Kenward-Roger approximation will be used to estimate the denominator degrees of freedom.

For subgroup analyses, the model will also include the subgroup variable as a covariate and the subgroup-by-treatment, subgroup-by-analysis visit and subgroup-by-analysis visit-by-treatment interactions. For details about subgroups please see Section 2.4.

A generalized MCP-Mod (1) approach at 1-sided alpha-level of 2.5% will be applied based on the estimated AUC treatment group effect and variance covariance matrix. Candidate models are given by the EMax (0.40428), Exponential (0.36411) and Linear model, with the aim to test for existence of drug-related effects. Each of the dose-response shapes in the candidate set will be tested using the corresponding contrast t-test statistic, employing a critical value derived for the maximum of the t-test statistics (based on the associated multivariate t-distribution) to ensure appropriate multiplicity correction that preserves a 1-sided 0.025 Type I error rate. A dose-response trend is established when the maximum of the t-test statistics exceeds the critical value.

MCP-Mod uses dose levels 0, 3 and 9 mg/kg which correspond to Placebo, Low and High dose respectively according to the dose/kg for age-group 3 as described in Section 1.2.

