Let the cumulative sample sizes for Cohort i up to analysis j be defined as n_{ij} :

	IA#1	IA#2	IA#3	IA#4	Final Analysis
Cohort 1 (n=144)	n_{11} (~36)	n_{12} (~75)	n_{13} (~144)	n_{14} (~144)	n_{15} (~144)
Cohort 2 (n=150)		n_{22} (~36)	n_{23} (~75)	n_{24} (~150)	n_{25} (~300)

RSV RNA Viral Load:

The total sample size planned for the primary analysis on viral load is given as: $n_{\text{Primary}}=294$. This constitutes the sample size of both Cohorts 1 and 2.

Stagewise weights and 1-sided p-values are defined as:

	IA#2	IA#3	IA#4
No enrichment:			
Weight	1		
p-value	p_{14}^F		
Final p-value (global)	p_{14}^F		
Final p-value (sub)	p_{14}^S		
Enrich at IA#2:			
Weight (w_{ij})	$(n_{12}+n_{22})/n_{\text{Primary}}$	$(n_{\text{Primary}} - n_{12} - n_{22})/n_{\text{Primary}}$	
p-value	p_{12}^F	p_{34}^S	
Final p-value (global)	$1 - \Phi \left(\sqrt{w_{12}} \Phi^{-1}(1 - p_{12}^F) + \sqrt{w_{34}} \Phi^{-1}(1 - p_{34}^S) \right)$		

	IA#2	IA#3	IA#4
Final p-value (sub)	$1 - \Phi \left(\sqrt{w_{12}} \Phi^{-1}(1 - p_{12}^S) + \sqrt{w_{34}} \Phi^{-1}(1 - p_{34}^S) \right)$		
Enrich at IA#3:			
Weight (w_{ij})	$(n_{13}+n_{23})/n_{Primary}$	$(n_{Primary}-n_{13}-n_{23})/n_{Primary}$	
p-value	p_{13}^F	p_{44}^S	
Final p-value (global)		$1 - \Phi \left(\sqrt{w_{13}} \Phi^{-1}(1 - p_{13}^F) + \sqrt{w_{44}} \Phi^{-1}(1 - p_{44}^S) \right)$	
Final p-value (sub)		$1 - \Phi \left(\sqrt{w_{13}} \Phi^{-1}(1 - p_{13}^S) + \sqrt{w_{44}} \Phi^{-1}(1 - p_{44}^S) \right)$	

- p_{ij}^F defines the p-value for the MCP-Mod test for data collected from in stages i to j in the full population
- p_{ij}^S defines the p-value for the MCP-Mod test for data collected from in stages i to j in the sub population

A p-value combination for the test of the sub-population is required, as the enrichment decision implies a sample size re-calculation for the sub-population.

Clinical Course Endpoints:

Sample size for clinical course endpoints is only based on Cohort 2. Let $n_{Primary} = 225$ be defined as midway between planned ($N= 150$) and maximum sample size ($N=300$).

	IA#2	IA#3	IA#4	Final Analysis
No enrichment:				
Weight (w_{ij})	$(n_{23})/n_{Primary}$		$(n_{Primary}-n_{23})/n_{Primary}$	
p-value	p_{23}^F		p_{45}^F	
Final p-value (global)	$1 - \Phi \left(\sqrt{w_{23}} \Phi^{-1}(1 - p_{23}^F) + \sqrt{w_{45}} \Phi^{-1}(1 - p_{45}^F) \right)$			

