- The conditional power at IA#4 is $<50\%$ to demonstrate antiviral activity of JNJ-53718678 compared with placebo based on the MCP-Mod trend test on viral load at 1-sided alpha=2.5% based on combined data from Cohort 1 and Cohort 2.

AND

- 80% 2-sided confidence interval on at least 2 key clinical course endpoints excludes effects as good as the TV based on data from Cohort 2 only

AND

- None of the 80% 2-sided confidence intervals on any key clinical course endpoint excludes effects as bad as the MAV based on data from Cohort 2 only

For viral load, the conditional probability of success at IA#4 using combined data from Cohorts 1 and 2 will be calculated assuming i) no enrichment and ii) enrichment as described below.

In both cases, the conditional probability of success will be set to 1 if the 1-sided p-value for the MCP-Mod trend test is less than 2.5% at IA#3, as success has already been reached. Otherwise, the conditional Type I error will be calculated using the inverse-normal combination approach:

$$\rho = 1 - \Phi \left(\frac{\Phi^{-1}(0.975) - \sqrt{w_1} \Phi^{-1}(1 - p_{Full})}{\sqrt{1 - w_1}} \right)$$

where:

- p_{Full} represents the 1-sided p-value for the MCP-Mod trend test for the full population at IA#3
- $w_1 = n_1 / n$
- n_1 represents the total number of randomized patients in Cohorts 1 and 2 at the time of IA#3
- $n = 294$, the planned total number of randomized patients in Cohorts 1 and 2 at IA#4

Given the conditional Type I error, the critical value for the MCP-Mod test based on new data from IA#4 only will be calculated. The conditional probability of success at IA#4 will be calculated under the observed test statistic at IA#3 (Z_1), adjusted for the sample size of the new data at IA#4 as:

$$CP_x = 1 - P(\bigcap_{i=1}^3 \{Z_{i,2} \in (-\infty, CRV)\})$$

where:

$$Z_2 \sim N \left(\mu_{Z,2} = \sqrt{\frac{n_2}{n_{1,x}}} Z_{1,x}, corr = corr_{MCPx} \right)$$

and:

- x corresponds to the decision not to enrich / to enrich at IA#3
- $Z_{1,x}$ represents the vector of observed MCP-Mod test statistics at IA#3 (Linear, Emax and Exponential models) based on the population of interest (full population for no enrichment and the sub-population with symptom onset ≤ 3 days for enrichment).
- Z_2 represents the vector of observed MCP-Mod test statistics for the second stage.
- $Z_{i,2}$ represents the observed MCP-Mod test statistic for the second stage (based on the new data at IA#4) for model i.

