
- $CP_{x;Stop} = 1 - \Phi \left(\frac{\Phi^{-1}(0.9) - \sqrt{w_1} \Phi^{-1}(1-p_{Full;TV})}{\sqrt{1-w_1}} - \sqrt{\frac{n_2}{n_{1,x}}} \Phi^{-1}(1-p_{x;TV}) \right)$

The conditional probability for the Go decision for the time to resolution of key RSV symptoms and the incidence of RSV-related complications will be calculated as:

- $CP_{x;Go} = \Phi \left(\min \{ CRV_{TV} - \mu_{x;TV}, \mu_{x;MAV} - CRV_{MAV} \} \right)$

where:

- $CRV_{TV} = \frac{\Phi^{-1}(0.9) - \sqrt{w_1} \Phi^{-1}(1-p_{Full;TV})}{\sqrt{1-w_1}}$ and $CRV_{MAV} = \frac{\Phi^{-1}(0.9) - \sqrt{w_1} \Phi^{-1}(1-p_{Full;MAV})}{\sqrt{1-w_1}}$
- $\mu_{x;TV} = \sqrt{\frac{n_2}{n_{1,x}}} \Phi^{-1}(1-p_{x;TV})$ and $\mu_{x;MAV} = \sqrt{\frac{n_2}{n_{1,x}}} \Phi^{-1}(1-p_{x;MAV})$
- x corresponds to the decision not to enrich / to enrich at #IA3
- $p_{x;TV}$ and $p_{x;MAV}$ represents p-values for the population of interest (full population for no enrichment and sub population for enrichment).
- $n_{1,x}$ represents the number of randomized patients in Cohort 2 at the time of IA#3 for the population of interest.

- n_2 represents the number of additional patients to be included in Cohort 2 up until the end of the study (i.e. $N - n_{1,Full}$, where N represents the total number of randomized subjects in Cohort 2 at the end of the study).
- $w_1 = n_1 / n_{Primary}$ where $n_{Primary} = 225$ is defined as midway between the planned sample size ($N=150$) and the maximum sample size ($N=300$) for Cohort 2.

The conditional probability of the Go decision for the change from baseline in key RSV symptoms at Day 8 needs to take the correlation, ρ , of Z_{TV} and Z_{MAV} into account.

$$\rho = -\frac{\left(\frac{1}{n_{H1,x}} + TV * MAV \frac{1}{n_{P1,x}}\right)}{\left(\sqrt{\frac{1}{n_{H1,x}} + TV^2/n_{P1,x}}\right)\left(\sqrt{\frac{1}{n_{H1,x}} + MAV^2/n_{P1,x}}\right)}$$

The conditional probability of the Go decision is calculated using a bivariate normal distribution where:

- $CP_{x;Go} = P(Z_{x2;TV} < CRV_{TV} \cap Z_{x2;MAV} > CRV_{MAV}; \mu = (\mu_{x;TV}, \mu_{x;MAV}), \rho)$

Where:

- $n_{H1,x}$ represents the number of Cohort 2 subjects in the high dose group that were included in the analysis at IA#3 for the population of interest.
- $n_{P1,x}$ represents the number of Cohort 2 subjects in the placebo treatment group that were included in the analysis at IA#3 for the population of interest.

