- $Z_{x2;TV}$ represents the test statistic to test the null hypothesis that the difference between the high dose and the placebo treatment group is at least as good as the target value (TV) at the end of the study (full population for no enrichment and sub population with symptom onset ≤ 3 days for enrichment).
- $Z_{x2;MAV}$ represents the test statistic to test the null hypothesis that the difference between the high dose and the placebo treatment group is no better than the minimum acceptable value (MAV) at the end of the study (full population for no enrichment and sub population with symptom onset ≤ 3 days for enrichment).

For all clinical course endpoints, the conditional probability of an inconclusive result will then be calculated as:

$$CP_{x;Inconclusive} = 1 - CP_{x;Stop} - CP_{x;Go}$$

Interim analysis 4

The IDMC will consider stopping the study for futility, if:

- Viral load did not meet success based on the MCP-Mod trend test at 1-sided alpha=2.5% based on combined data from Cohort 1 and Cohort 2

AND

- 80% 2-sided confidence interval on at least 2 key clinical course endpoints excludes effects as good as the TV based on data from Cohort 2 only

AND

[figure not shown]
- None of the 80% 2-sided confidence intervals on any key clinical course endpoints excludes effects as bad as the MAV based on data from Cohort 2 only

For IA#3 and IA#4 two separate tests for two study populations are conducted and no formal multiplicity adjustments for the multiple study populations were implemented.

- Test for full population
- Test for subpopulation of patients ≤ 3 days since symptom onset

The futility rules defined are applied to each population separately. For decision-making, results of both populations will be considered. The following figure (refer to [Figure 3: Decision Flowchart](#)) provides an overview of the decision rules based on different endpoints to determine whether to stop the study for futility. Study will be stopped for futility if futility is reached in both populations.

Figure 3: Decision Flowchart

TV- Target value; MAV -Minimum Acceptable Value

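### The IA#3 conditional power with enrichment uses the full-population stage-1 p-value, so it fits only the global test and leaves the ≤3-day futility rule without a matching value

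*SAP*

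**What the plan says.** **Viral load (Section 5.6, Interim analysis 3).** One conditional error, rho, serves both scenarios. Its stage-1 input is p_Full, which "represents the 1-sided p-value for the MCP-Mod trend test for the full population at IA#3", with weight w1 = n1/294. The stage-2 part (test statistics, stage-1 sample size, correlation matrix) changes with the scenario: full population without enrichment, ≤3-day population with it. Conditional power is set to 1 if the IA#3 MCP-Mod p-value is already below 2.5%; the population of that p-value is not named.

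**Clinical endpoints (same section).** The drift uses p_x, which "represents p-values for the population of interest (full population for no enrichment and sub population for enrichment"). CRV_TV and CRV_MAV use p_Full;TV and p_Full;MAV in both scenarios. The section also has p_Sub;TV and p_Sub;MAV estimated, so the ≤3-day inputs are available.

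**Final tests (Section 5.2.3.2).** After enrichment at IA#3 there are two final p-values. The global one combines the full-population stage-1 p-value with the ≤3-day stage-2 p-value. The sub one uses ≤3-day p-values at both stages, because "A p-value combination for the test of the sub-population is required, as the enrichment decision implies a sample size re-calculation for the sub-population".

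**Use of the results.** At the end of Section 5.6 the full and ≤3-day populations are tested separately at IA#3 and IA#4 without multiplicity adjustment, and "The futility rules defined are applied to each population separately"; the study stops only if both are futile. Section 2.4 adds that after an enrichment decision "efficacy analyses will focus on those subjects with symptom onset" of three days or less. The enrichment trigger is conditional power below 50% on at least two of four endpoints; no scenario is named for it.

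**The concern.** A futility rule applied to the ≤3-day population needs the probability that the ≤3-day test will succeed. Section 5.6 gives no such quantity. The only conditional power that uses ≤3-day data takes its critical value from the full population, so results in the >3-day stratum set the hurdle for a test that contains none of those children.

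The error depends on how the strata differ. If the early-onset children do better than the whole, p_Full is worse than p_Sub and the value is too low for the ≤3-day test. If they do worse, it is too high. The two versions part when the strata disagree, which is when a separate ≤3-day check is of use.

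**Working it through.** **Check of the MCP-Mod set-up.** The SAP prints no conditional power. Its Table 1 power figures were recomputed instead, from these inputs:
- Section 5.1.1: "The dose-response will be tested at each (interim) analysis at alpha=2.5% (1-sided").
- Section 5.2.3: "Candidate models are given by the EMax (0.40428), Exponential (0.36411) and Linear model".
- Section 5.2.3: "MCP-Mod uses dose levels 0, 3 and 9 mg/kg which correspond to Placebo, Low and High dose respectively".

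For 74 per arm, CV 35% and a 20% reduction, the result is 92.6/95.5/96.7% (linear/Emax/exponential), against 92.3/95.3/96.6% in Table 1. All 18 entries agree within 0.5 points.

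**Inputs for conditional power.**
- Section 5.2.3.2: about 144 in Cohort 1 and 75 in Cohort 2 at IA#3, so n1 = 219.
- Section 5.6: n = 294, so n2 = 75 and w1 = 219/294 = 0.745; √w1 = 0.863 and √(1−w1) = 0.505.
- Assumption: 110 of the 219 are ≤3 days. Section 1.2 requires at least 45% of enrolled subjects, which would be about 99.
- Assumption: the p-values below are illustrative.

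**Formula (single-contrast approximation).** CP = 1 − Φ(c − d), with c = (1.960 − 0.863·z1)/0.505 and d = √(75/110)·z_Sub = 0.826·z_Sub. Here z1 comes from p_Full as the SAP is written, or from p_Sub for the ≤3-day test.

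**Case 1: p_Full = 0.20 (z = 0.842), p_Sub = 0.03 (z = 1.881).** d = 1.553.
- As written: c = 2.442, CP = 1 − Φ(0.889) = 19%.
- ≤3-day test: c = 0.667, CP = 1 − Φ(−0.886) = 81%.

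**Case 2: p_Full = 0.03, p_Sub = 0.20.** d = 0.695.
- As written: c = 0.667, CP = 1 − Φ(−0.028) = 51%.
- ≤3-day test: c = 2.442, CP = 1 − Φ(1.747) = 4%.

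With 99 children ≤3 days the figures are 21% against 83% and 53% against 4%.

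**Which test the formula fits.** In case 1, rho = 1 − Φ(2.442) = 0.0073. A stage-2 p-value of exactly 0.0073 gives:
- global: 0.863·0.842 + 0.505·2.442 = 1.960, final p = 0.025;
- sub: 0.863·1.881 + 0.505·2.442 = 2.857, final p = 0.002.

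So rho is exact for the global test and is not the conditional error of the sub test.

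**Full three-model calculation.** Assumed standardised high-dose effects, Emax shape, 110 children ≤3 days:
- Effect 0.45 in ≤3 days and 0 in >3 days (p_Full 0.113, p_Sub 0.030): 43% as written, 83% with p_Sub.
- Effect 0.30 in both strata (p_Full 0.040, p_Sub 0.130): 56% as written, 19% with p_Sub.

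**Clinical endpoints, MAV part only.** Cohort 2 has 75 at IA#3 and w1 = 75/225; assume 37 children ≤3 days and total N = 150, so n2 = 75. Take p_Full;MAV = 0.05 and p_Sub;MAV = 0.40. The drift is √(75/37)·0.253 = 0.361.
- As written: CRV_MAV = (1.282 − 0.577·1.645)/0.816 = 0.406; Φ(0.361 − 0.406) = 48%.
- With p_Sub;MAV: CRV_MAV = (1.282 − 0.577·0.253)/0.816 = 1.390; Φ(0.361 − 1.390) = 15%.

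The Go probability also depends on the TV part, so both figures are upper bounds on it.

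**The case against.** The strongest defence is that the formula is exact for a pre-specified test, the global one. That stands, and a reader who infers that the formula is simply wrong goes too far. If success after enrichment required both final tests, conditional power for viral load would be the smaller of the two values, because the tests share weights and the stage-2 p-value. Whenever p_Sub is below p_Full that minimum is the SAP value, so case 1 would show no error. Case 2 still would: the minimum is 4%, not 51%. The SAP does not say whether global, sub or both define success.

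A reader might also infer that the enrichment decision rests on this quantity. The SAP does not establish that. The trigger names no scenario, and the no-enrichment value, where p_Full is correct, is a natural reading.

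Nor would the mismatch by itself stop the trial. At IA#3 futility needs low viral-load conditional power together with two confidence-interval conditions that do not use these p-values. It must be reached in both populations, and the IDMC only considers stopping.

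The set-to-1 rule would also bypass the formula in some discordant cases, depending on which population's p-value it means. Finally, Section 5.2.3.2 calls the combination test a secondary approach. Section 5.6 nevertheless builds this conditional power on it, and no ≤3-day test, combined or not, has >3-day children in its stage-1 data.

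**Conclusion.** The point holds in limited form. The with-enrichment conditional power at IA#3 is that of the global test only. The SAP defines none for the separate ≤3-day test to which it applies the viral-load futility rule, nor for the sub final p-value. If the existing value is used there, it can fall on the wrong side of 50% in either direction: 19% against 81%, and 51% against 4%. These sizes rest on illustrative p-values, an assumed 110 of 219 children ≤3 days and a single-contrast approximation. The three-model calculation shows the same pattern. No claim is made about how often such p-values would occur, and the final p-values themselves are unaffected.

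**What to change.** In Section 5.6:
1. For the ≤3-day population, compute rho, CRV_TV and CRV_MAV from p_Sub, p_Sub;TV and p_Sub;MAV with the same weights, and use that viral-load value in the ≤3-day futility rule.
2. State whether success after enrichment means the global test, the sub test or both. If both, use the smaller viral-load conditional power, and for the clinical endpoints the joint Go probability.
3. Apply the set-to-1 rule with the p-value of the same population.
4. Keep the p_Full version, labelled as global conditional power.
5. State that the low-conditional-power trigger for enrichment uses the no-enrichment value, and show the with-enrichment value beside it. The p_Sub-based value should not be the trigger, because it would work backwards. In case 1 it is 81% and would not count toward enriching, although the drug appears to work early only. The no-enrichment value, with drift √(75/219)·0.842 = 0.493, is 1 − Φ(2.442 − 0.493) = 2.6% and would count.

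The cost is a few lines in Section 5.6 and one changed argument in the IA#3 program. It should be settled before IA#3 results are seen, since a later choice would be driven by the data.
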